### **5.2. Study Procedures**

Following is a detailed list of study visits from screening to discharge and the required procedures/tests.

#### **5.2.1. Informed Consent**

Prior to recruitment of any subjects into the study, written approval of the CIP and informed consent must be obtained from the Ethics Committee (EC) and Competent Authority (CA).

Pre-screening, i.e., medical record review without obtaining informed consent, is allowed.

Informed consent must be obtained from each subject prior to conducting any study-related tests or procedures, including screening procedures.

The investigator will explain the study purpose, procedures, and subject's responsibilities to the potential participant. The subject's willingness and ability to meet the study requirements will be determined, and written informed consent will be obtained. The subject will sign and date the informed consent form. The investigator will also sign and date the consent form. The

original informed consent form will be retained with the subject records. A copy of the informed consent will be provided to the subject.

A subject is considered enrolled after informed consent has been obtained.

### 5.2.2. Subject Identification

To maintain confidentiality, the subject’s name will not be recorded on any study document other than the informed consent form. Each enrolled subject will be pseudonymized and assigned a unique identifier in the following format: CCC-SSS-PPP. CCC is the Country code (same as Tel.) SSS is the site number and PPP is the 3-digit sequential subject ID number starting with 001. For example, the first subject in CZ at site 001 will be assigned 420-001-001. Subject ID numbers will not be re-used (e.g., if the subject is determined to be a screen failure).

### 5.3. Study Visits

#### 5.3.1. Schedule of Assessments and Visits

	Visit 1 Screening Max 30 days before index EP procedure	Visit 2 Index EP procedure	Visit 2 Discharge
Informed Consent	✓		
Demographics	✓		
Cardiac Medical History	✓		
Arrhythmia History	✓		
Cardiac Medications	✓	✓	✓
Inclusion/Exclusion	✓		
12 lead ECG	✓		✓
Urine Pregnancy Test*	✓		
EP procedure		✓	
Adverse Events		✓	✓
Device Malfunctions		✓	
Protocol Deviations	✓	✓	✓

\* Women of child-bearing potential only Max 7 days before Index EP Procedure (Visit 2)

#### 5.3.2. Visit 1: Screening Visit

Screening will be completed within 30 days of the index EP procedure date.

Test results from routinely performed standard assessments may be used to determine eligibility. Pre-screening will consist of a review of relevant medical history including duration and frequency of arrhythmia(s), their subsequent treatments (e.g., medications, previous ablation) and associated symptoms.

---

If pre-screening criteria are met, informed consent will be obtained, and screening will proceed. Eligibility will be assessed sequentially, starting with the least invasive and least expensive tests as follows. Results from each test or screening activity should be reviewed prior to proceeding to the next step.

- Demographics
- Cardiac medical history
- Arrhythmia history (TTM, EKG, Holter, etc.)
- Cardiac medications
- In / Exclusion criteria
- 12-lead ECG
- Pregnancy test (pre-menopausal women only, within 7 days of index EP procedure)
- Protocol deviations
- 

### **5.3.3. Screen Failures**

Subjects not meeting all study entry criteria will be designated as screen failures. End of study procedures will not be performed for these subjects, but their reason for ineligibility will be recorded on the Screening Log. Screen failures are counted towards the total study enrollment.

### **5.3.4. Visit 2: Index Procedure through Discharge**

During the index EP procedure, only procedures or steps from institutional standard of care / best practice will be used to treat the subjects.

When the subject is connected to the standard EP recording system, during manipulation of catheters or diagnostic tests, intracardiac signals will be recorded using the investigational device in parallel. It is not expected to cause any significant delays to the total procedure time as the final comparison of data recorded from Standard EP recording system and the tested device will happen post procedure.

Index EP procedure, the following will be documented

- EP data recording
- Change in cardiac medication
- Adverse events and device malfunctions
- Protocol deviations

Prior to discharge, the following will be documented:

- 12 lead ECG will be performed
- Change in cardiac medications
- Adverse events
- Protocol deviations

All subjects will exit the study after this visit.

## **5.4. Study Completion**

### **5.4.1. Completed Subjects**

---

Subjects will be considered complete when all assessments through the Discharge have been performed in accordance with the CIP.

#### **5.4.2. Discontinued Subjects**

Any subject may voluntarily discontinue the study at any time without prejudice. The investigator may discontinue a subject from the study at any time if (s)he considers that remaining in the study compromises the subject's health or the subject is not sufficiently cooperative. In either event, reason(s) for discontinuation should be recorded.

Possible reasons for study discontinuation include the following:

- Adverse events (AEs) necessitating discontinuation from the study
- Subject decision (specify)
- Investigator decision (specify)
- Other reason (specify)

The reasons for any subject discontinuation will be recorded on the study completion form of the study CRF. If possible, subjects who withdraw prior to study completion will undergo the following:

- AE assessment
- Device malfunction, if applicable

#### **5.4.3. Premature Study Termination**

The Sponsor, Investigators, Ethics Committee, or Competent Authority have the right to suspend or terminate the study prematurely for any safety, ethical or administrative reason at any time.

The study will be suspended or prematurely terminated if, in the opinion of the Principal Investigator (PI), Sponsor, reviewing EC or Competent Authority, the safety of subjects and/or data is uncertain. The Sponsor should make sure that the suspension or premature termination will be communicated through the PI, Competent Authority and reviewing EC.

Possible reasons for suspending/terminating a study center include but are not limited to:

- Failure to obtain written Informed Consent
- Failure to report SAEs/SADEs to Sponsor within 24 hours of knowledge
- Loss of (or unaccounted for) investigational product inventory
- Repeated protocol deviations
- Repeated failure to complete case report forms prior to scheduled monitoring visits

In the event of premature study termination, a written statement as to why the premature termination has occurred will be provided to the study site by CathVision ApS. The EC and the Competent Authorities will be notified. Detailed information on how enrolled subjects will be managed thereafter will be provided.

In the event an EC terminates participation in the study, participating study site and Competent Authorities will be notified in writing. Detailed information on how enrolled subjects will be managed thereafter will be provided by CathVision ApS.

---

In the event the investigator terminates participation in the study, study responsibility will be transferred to a co-investigator when possible or another authorized Investigator. In the event there are no opportunities to transfer investigator responsibility; detailed information on how enrolled subjects will be managed thereafter will be provided by CathVision ApS (Sponsor).

The investigator must return all documents and investigational product to Sponsor, unless this action would jeopardize the rights, safety, or welfare of the subjects.

Sponsor reserves the right to stop the inclusion of subjects at a study site at any time if no subjects have been enrolled for a period beyond 3 months after the site has been granted approval to enroll, or if the study site has multiple or severe protocol deviations/noncompliance without justification and/or fails to follow remedial actions.

In the event of termination of investigator participation, all study-related devices and equipment, as applicable, will be returned to Sponsor unless this action would jeopardize the rights, safety or well-being of the subjects. The EC and Competent Authorities will be notified.

## **5.5. Investigational Device Accountability**

Documentation of receipt, use and return of the CathVision Cube® System and its parts must be maintained by the Principal Investigator (PI) or his/her Designee in a device accountability log. Investigational devices are to be used only in accordance with this CIP and under supervision of the PI or a duly designated person. It is the PI's responsibility to ensure that all study devices are kept in a secure location, with access limited to individuals authorized by the investigator. A record of all study devices (by their lot or serial numbers) received, used and returned must be maintained by the site until the conclusion of the study. Following accountability of the study devices by the Sponsor or its Designee, all unused study devices will be returned to the Sponsor/Designee as directed in writing by the Sponsor or Designee for gross reconciliation.

## **6. Examinations and Evaluations**

### **6.1. Demographics**

Date of birth, gender, race and ethnicity will be recorded.

### **6.2. Cardiac and Arrhythmia Medical History**

Relevant cardiac and arrhythmia medical history including duration and frequency of arrhythmia(s), their subsequent treatments (e.g., medications, previous ablation) and associated symptoms will be obtained at Screening. All positive and negative findings will be carefully documented. Any new finding discovered during the Screening evaluation and prior to the index EP procedure will be considered to be part of the medical history and will not be recorded as an AE.

### **6.3. Cardiac Medications**

Cardiac medications (including antiarrhythmic drugs) will be recorded at each visit, including medications prior to the visit and medications prescribed during the visit. For each medication, the following information will be collected:

- Medication trade or generic name

- 
- Indication for which the medication was given
  - Dose/strength, route, and frequency of administration
  - Date started
  - Date stopped (or continuation at study exit)

#### **6.4. 12-Lead ECG**

A 12-lead electrocardiogram (ECG) will be conducted. The ECG recording will be printed out, and a copy will be placed with subject records. Any clinically significant abnormalities will be recorded.

#### **6.5. Pregnancy Test (women of childbearing potential only)**

For women of childbearing potential, a urine beta human chorionic gonadotropin ( $\beta$ -HCG) test will be performed at Screening, and again if undergoing a remapping procedure. Results of the test must be negative. Confirmed menopause is defined as postmenopausal for  $\geq 1$  year.

### **7. Safety Reporting and Device Deficiencies**

#### **7.1. Adverse Events Definitions**

An **adverse event (AE)** is the development of an untoward medical occurrence or the deterioration of a pre-existing medical condition following or during exposure to an investigational medical device, whether or not considered causally related to the investigational medical device.

An untoward medical condition can be symptoms (e.g., nausea, chest pain), signs (e.g., tachycardia, enlarged liver) or clinically significant abnormal results of an investigation (e.g., laboratory findings, electrocardiogram).

Conditions or diseases that are chronic but stable should not be recorded as an AE. Changes in a chronic condition or disease that are consistent with natural disease progression are NOT considered AEs and should not be recorded. These medical conditions should be adequately documented in the subject's medical history. However, medical conditions present at enrollment that worsen in intensity or frequency in a manner inconsistent with the natural course of the disease during the treatment or post-treatment periods should be reported and recorded as AEs.

A recurrence of an atrial tachyarrhythmia requiring hospitalization in order to administer cardioversion within the blanking period is within the scope of treatment for chronic but stable AF subjects. This will not be considered an adverse event. Self-limiting pericarditis attributable to the EP procedure, defined as pleuritic chest discomfort with or without pericardial rub and ECG changes, is not considered an adverse event.

A **serious adverse event (SAE)** is any untoward medical occurrence which:

- Results in death, permanent impairment of a body function or permanent damage to a body structure;

- 
- Results in serious deterioration in the subject's health that either:
    - Is life-threatening;
    - Requires inpatient hospitalization (admission to hospital with a stay > 24 hours) or prolongation of hospitalization which is not specifically required by the CIP or is elective;
    - Results in permanent impairment of a body function or permanent damage to a body structure; or
    - Requires medical or surgical intervention to preclude permanent impairment of a body function or permanent damage to a body structure.

Additionally, important medical events that may not result in death, be life-threatening or require hospitalization may be considered SAEs when they jeopardize the subject or require medical or surgical intervention to prevent one of the serious outcomes listed above.

**Adverse device effect (ADE)** is an AE related to the use of an investigational medical device. Note, this definition includes AEs resulting from insufficient or inadequate instructions for use, operation, or any malfunction of the investigational medical device. In addition, this definition includes any event resulting from use error or from intentional misuse of the investigational medical device.

**Serious adverse device effect (SADE)** is an ADE that that has resulted in any of the consequences characteristic of a SAE.

An **unanticipated adverse device effect (UADE)** is defined as any serious adverse effect on health or safety or any life-threatening problem or death caused by, or associated with, a device, if that effect, problem, or death was not previously identified in nature, severity, or degree of incidence in predicate devices, or any other unanticipated serious problem associated with a device that relates to the rights, safety, or welfare of subjects.

## 7.2. Assessment of Adverse Events

The need to capture AEs is not dependent upon whether or not the clinical event is associated with the use of the study device or procedure. All AEs, regardless of severity, occurring at the index EP through study exit visit must be recorded. Events occurring prior to the endovascular procedure must be listed in the medical history.

Any Adverse Event(s) that may occur in this study needs to be reported directly to the Sponsor and the EC, as applicable. Participants experiencing Adverse Events must be treated by the investigator per clinical standard practice at the hospital.

The following information should be obtained for each AE:

1. **Event description.** Every effort must be made to report the underlying condition or unifying diagnosis for the event. To avoid vague, ambiguous or colloquial expressions, the AE should be recorded in standard medical terminology rather than the subject's own words when possible. Signs and symptoms that are considered unrelated to an encountered syndrome or disease should be recorded as individual AEs on the CRF (e.g., if congestive heart failure and severe headache are observed at the same time, each event should be recorded as an individual AE).

---

In addition, AEs occurring secondary to other events (e.g., sequelae) should be identified by the primary cause (i.e., a "primary" AE, if clearly identifiable, generally represents the most accurate clinical term to record on AE CRF; events occurring secondary to the primary event should be described in the narrative description of the case [e.g., example: orthostatic hypotension → fainting and fall to floor → head trauma → neck pain; the primary AE is orthostatic hypotension]).

2. **Duration:** The date of onset and date of resolution should be reported. Every effort should be made to capture the exact dates.
3. **Outcome:** The final status of the event should be reported as resolved, ongoing, or if it resulted in death. If the event is present at the final study visit, the ongoing box must be marked.
4. **Severity:** The worst severity of the event must be reported as mild, moderate, or severe using the following definitions:
  - **Mild:** Aware of sign or symptom, but easily tolerated
  - **Moderate:** Discomfort enough to cause interference with usual activity
  - **Severe:** Incapacitating with inability to work or do usual activity
5. **Action taken:** Treatment of the event may be reported as none, medical and/or surgical.
6. **Seriousness:** Determined by using the criteria in Section 7.1.
7. **Relationship to device (study device or ancillary device), and procedure.** The relationship to device and study procedure will be assessed using the following criteria.
  - **Not related:** no temporal association, or the cause of the event has been identified; or the device or procedure cannot be implicated
  - **Unlikely:** the relationship with the use of the device seems not relevant and/or the event can be reasonably explained by another cause, but additional information may be obtained
  - **Possible:** temporal association, but other etiologies are likely to be the cause; however, involvement of the device or procedure cannot be excluded
  - **Probable:** the relationship with the use of the investigational device seems relevant and/or the event cannot reasonably be explained by another cause, but additional information may be obtained
  - **Causal:** temporal association; other etiologies are possible, but unlikely

If any AE is considered to be “possibly related” or “related” to the use of the study device, that event will be classified as an ADE or a SADE.

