## 3. Risk-Benefit Analysis

There are no known risks to the potential subjects specifically associated with the use of the CathVision Cube® System.

Potential subject risks include adverse events and potential product failures similar to commercially available EP recording systems, with a similar likelihood of occurrence.

Potential device malfunctions and potential user errors have been identified in the Hazard Analysis and Failure Modes and Effects Analysis exercises conducted in accordance with ISO 14971. These are technical complications that may occur with the devices. Mitigating steps to address each of the potential device malfunctions and potential user errors have been implemented to reduce the risks as low as possible. No residual risks remain that are higher than the risks associated with the use of currently available conventional cardiac electrophysiology and catheter ablation tools. A list of device deficiencies and malfunction are defined in section 7.7 of this document.

The anticipated adverse events associated with cardiac electrophysiology procedures include events reported in the literature related to catheter procedures, events identified in the risk and hazard analyses, and events associated with percutaneous interventions, and therefore represent the risks associated with participation in the study. A list of anticipated adverse events is defined in Section 7.6 of this document. Each adverse event or device effect will be evaluated in detail as described in Section 7 of this document.

The CIP is designed for parallel data collection during electrophysiology study and investigator diagnostic decisions will be guided by an approved EP recording system. Due to this CIP design and noninvasive nature of the tested medical device there is expected a low rate of occurrence of SAEs or SADEs related to use of investigational device. CathVision personnel will be responsible for operation and installation of the tested device.

The potential patient benefits include reduction in symptomatic episodes of arrhythmia due to possible better interpretation of EP signals using the CathVision Cube® system. As the treatment will be guided by an approved EP recording system the reduction in symptomatic arrhythmia will be similar to the benefit of currently available EP recording systems.

---

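### Could the wording of the *Possible* causality level turn EP-procedure complications into effects of the study device?

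*Protocol*

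**What the plan says.** Protocol section 7.2, item 7, is headed "Relationship to device (study device or ancillary device), and procedure" and gives one set of five levels for these relationships. The levels do not all name the same thing:

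- *Not related* and *Possible* refer to the device or the procedure. *Not related* includes "no temporal association, or the cause of the event has been identified"; *Possible* includes "involvement of the device or procedure cannot be excluded".
- *Unlikely* refers to the device, and covers the case where "the event can be reasonably explained by another cause".
- *Probable* refers to the investigational device: "the relationship with the use of the investigational device seems relevant".
- *Causal* names neither.

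The sentence after the list gives the label to events rated possibly related or related "to the use of the study device, that event will be classified as an ADE or a SADE". The word *related* is not one of the five levels. Section 7.1 defines an ADE through the investigational device and does not mention the procedure.

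Section 7.5 anticipates no adverse event specific to the system, while section 7.6 gives a long list of events anticipated from the EP procedure.

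**The concern.** The study has one arm, and every subject undergoes an invasive procedure while the investigational system records passively. The relatedness rating is therefore the only step that separates device effects from procedural ones. Almost all anticipated events are procedural. If the lowest ADE-triggering level can be met by the procedure, a complication such as a groin haematoma might be tabulated as an effect of the recording system at one site and not at the other.

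The risk-benefit case in section 3 is specific to the device: "there is expected a low rate of occurrence of SAEs or SADEs related to use of investigational device". An ADE count inflated by procedural events would obscure that claim. Section 3 also states that "CathVision personnel will be responsible for operation and installation of the tested device", and section 7.4.2 makes the sponsor responsible for classifying adverse events. A rule that leaves room for interpretation is then less comfortable than it would be with an independent classifier.

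**Working it through.** The plan states no figure on this point, so the check is mainly a comparison of texts.

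**Step 1. Apply *Possible* to a complication that the procedure probably caused.** The level has two parts: other causes are likely, and involvement cannot be excluded. Each part needs a referent.

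| Reading | Other causes likely? | Involvement not excludable? | Result |
|---|---|---|---|
| Both parts refer to whichever item is being rated (here the study device) | Yes: the procedure is the other cause | Only if the study device itself cannot be excluded | ADE only where the device is genuinely in question |
| Both parts refer to device and procedure merged | No: the procedure is the likely cause, so no other cause is likely | Yes, through the procedure | *Possible* not met; the event rates higher, and the ADE sentence still asks about the study device |
| First part refers to the device, second to device or procedure | Yes | Yes, through the procedure | *Possible*, hence ADE |

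Only the third reading produces the error, and it changes referent in mid-sentence.

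**Step 2. Add the surrounding text.** Item 7 names two relationships to be assessed with the same criteria, so the natural sense of device or procedure is the one being rated. The ADE sentence and the section 7.1 definition are both confined to the study device. For deaths, section 7.4.1 asks for the relationship to the investigational device. Read together, an event possibly related to the procedure alone is not an ADE.

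**Step 3. Trace what depends on the label.**

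- *Endpoint.* The safety endpoint (synopsis and section 5.1.1) concerns adverse events and device malfunctions. It does not name ADEs.
- *Capture.* Section 7.2 requires every adverse event from the index procedure to study exit to be recorded, related or not. The total does not move.
- *Reporting.* Section 7.4.1 sends all SAEs to the ethics committee and, within 24 hours, to the sponsor. Section 7.4.2 sends all SAEs to the competent authorities. Section 9.4 mentions informing the ethics committee of SADEs, but does not limit reporting to them.
- *Decision rules.* Section 8.1 has no hypothesis, and section 8.2 has no statistical criterion for terminating the study.

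**Step 4. Scale.** The protocol gives no procedural complication rate, so the rate r is assumed. With n = 30 (the stated maximum), the expected number of subjects is 30r, and the chance of at least one is 1 − (1 − r)^30.

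| Assumed r | Expected subjects | Chance of at least one |
|---|---|---|
| 1% | 0.3 | 26% |
| 3% | 0.9 | 60% |
| 5% | 1.5 | 79% |
| 10% | 3.0 | 96% |

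These are subjects in whom the question could arise. They are not predicted ADEs, because mislabelling would also need the third reading in step 1.

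**The case for a change.** The best case for a change is that the sensible reading is not written down. *Probable* names only the investigational device, so the scale does not consistently adapt to the item being rated, and section 7.2 never says that device and procedure receive separate ratings. If a form recorded one combined rating, a procedural event could be carried into the ADE class by inattention. The levels also overlap even when only the device is rated: an event with another reasonable explanation, in which the device still cannot be ruled out, fits both *Unlikely* and *Possible*, and the ADE boundary lies between them. Finally, *Probable* and *Causal* fall under *related* only by natural reading.

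All of this stands as criticism of the drafting. What it shows is a chance of inconsistent labelling, not a rule that misattributes events. The overlap between adjacent levels calls for clinical judgement. An error through the *Possible* wording would over-attribute events to the device, which is the cautious direction for safety. The length of the list in section 7.6 adds little: it counts terms, several of which overlap, and many such events will have an identified cause, which is *Not related* for the device.

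**Conclusion.** The concern does not hold as a fault in the plan. The scale is loosely worded, but the ADE sentence and the section 7.1 definition confine the label to the study device, and a consistent reading of *Possible* does not let the procedure alone satisfy it. What is left is a detail that investigators, or a form with separate device and procedure fields, would settle in the ordinary course.

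The possible effect is small: at most a few events (0.3 to 3.0 subjects expected among 30, at assumed rates of 1% to 10%) might carry a different relatedness label. The adverse event total, SAE reporting and the safety endpoint would be the same either way.

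This rests on two conditions. The case report form is not shown, and it is assumed that it, or the investigator, rates device and procedure separately. It also depends on no success criterion or stopping rule being tied to an ADE count; the protocol contains none.

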## **7.4. Adverse Events Requiring Expedited Reporting**

### **7.4.1. Investigator Responsibilities**

The Investigator is responsible for reporting all SAEs, SADEs, and device deficiencies that could have led to a SADE to the EC, according to national regulations and EC requirements. The investigator will forward a copy of this report to the Sponsor and file it in the investigator site binder.

The Investigator will document all SAEs and SADEs, including device deficiencies in the study subject's file and report it to the Sponsor and to the Sponsor's (Designee) within 24 hours of knowledge of event. When medical reports (lab results, examinations, etc.) associated with AEs are submitted to the Sponsor or Sponsor's Designee, all personal subject information (name, address, etc.) *must* be removed or redacted. The redacted materials must be identified only with the subject ID number.

In the event of a subject's death, the Investigator will make reasonable effort to obtain a copy of the autopsy report and/or death summary. The Investigator will determine the cause of death and its relationship to the investigational device; the Investigator will record results on the AE case report form (CRF). The Investigator will include copies of an autopsy report, if available, and/or a death summary with this form.

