### **7.4.2. Sponsor Responsibilities**

Upon notification of SAEs, the Sponsor will initiate and complete a review and evaluation of the event within time frames that will maintain reporting compliance with applicable regulatory agencies. The Sponsor is responsible for classification and reporting of AEs and ongoing safety evaluation of the clinical investigation in line with EN ISO 14155:2012 and regulatory requirements. If insufficient information is available to reach a definitive diagnosis, the Sponsor may instruct the CRA responsible for the site to contact the site to request additional confirmatory information, if any.

The Sponsor will ensure that its Designee will report all SAEs and device deficiencies that could have led to an SADE to the Competent Authorities in accordance with European Medical Devices Directive and all applicable national regulations including the medical device act of the Czech Republic and Denmark.

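### Does the mismatch between the causality scale and the ADE/SADE rule in Protocol 7.2 leave Probable and Causal events unclassified?

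*Protocol*

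**What the plan says.** Section 7.2, item 7, sets one five-level scale for the relationship to the device and to the procedure: Not related, Unlikely, Possible, Probable, Causal. The classification rule comes directly after it and opens "If any AE is considered to be “possibly related” or “related” to the use of the study device"; such an event becomes an ADE or a SADE.

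The two top levels are defined as follows:

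- Probable: "the relationship with the use of the investigational device seems relevant and/or the event cannot reasonably be explained by another cause", with a rider that more information may still be obtained.
- Causal: "temporal association; other etiologies are possible, but unlikely".

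Section 7.1 defines an ADE separately: it "is an AE related to the use of an investigational medical device". A SADE is an ADE with a serious consequence.

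On capture and reporting, section 7.2 states "The need to capture AEs is not dependent upon whether or not the clinical event is associated with the use of the study device". Section 7.4.1 states "The Investigator is responsible for reporting all SAEs, SADEs, and device deficiencies that could have led to a SADE to the EC". Under section 7.4.2 the sponsor's designee "will report all SAEs and device deficiencies that could have led to an SADE to the Competent Authorities". The same section makes the sponsor responsible for classifying adverse events.

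**The concern.** The rule puts its two trigger terms in quotation marks, as if they were categories, yet neither is a label on the scale that precedes it. *Possibly related* is close to Possible. *Related* is not a level at all, and section 7.1 repeats the word without tying it to one. On a strict reading, a Possible event becomes an ADE while a Probable one, with a stronger link to the device, does not.

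The top of the scale adds to the doubt. Causal tolerates other causes if they are unlikely. Probable can mean that no other cause reasonably explains the event. One event can meet both definitions, and on alternative causes the highest level is no stricter than the one below it.

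What would be at stake is the count of device effects. This is a single-arm study of patients whose EP procedures carry a long list of anticipated complications (section 7.6), so attribution is the main way to separate device from procedure. Section 3 also rests on an expectation about related events: "there is expected a low rate of occurrence of SAEs or SADEs related to use of investigational device". With up to 30 subjects, one reclassified subject would move a subject-level ADE proportion by at least 1/30 = 3.3 percentage points.

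**Working it through.** The protocol gives no figure to reproduce, so the check is a comparison of texts.

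**Step 1: match the scale to the rule, using one method throughout.**

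| Level (7.2) | Sense of the definition | Label appears as a trigger? | Covered in sense? |
|---|---|---|---|
| Not related | device or procedure not implicated | no | no |
| Unlikely | another cause reasonably explains it | no | no |
| Possible | other causes likelier, device not excluded | no | yes, *possibly related* |
| Probable | link to the device appears relevant | no | yes, *related* |
| Causal | timing fits, other causes unlikely | no | yes, *related* |

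By exact label the rule captures 0 of 5 levels, which would make it empty. By sense it captures 3 of the 3 positive levels. The result that Possible counts and Probable does not (1 of 3) arises only if Possible is matched by sense while Probable and Causal are held to their labels. A result of 2 of 3 requires *related* to mean Causal alone, so that the rule skips a level in the middle of an ordered scale.

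**Step 2: ask which reading the protocol supports.** Three features point to Possible or higher.

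- The rule already admits Possible, where other causes are thought likelier. A rule that admits the weaker link cannot sensibly refuse the stronger.
- The lowest level is Not related, so *related* is its natural opposite.
- Probable is defined by a relevant relationship with use of the device, and section 7.1 makes an event related to use of the device an ADE. Probable events therefore qualify through 7.1 as well.

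**Step 3: does the overlap matter?** Probable and Causal both lie above the cut-off. An event that could be rated either way is an ADE both times. Only the recorded causality category can differ, and nothing in the protocol uses that distinction.

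**Step 4: follow the consequences.**

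- *Recording:* all adverse events are recorded from the index procedure to study exit, each with its relationship rating (7.2, 7.3). An ADE table can be rebuilt from the ratings under any cut-off.
- *Expedited reporting:* every SADE is also an SAE, and all SAEs go to the ethics committee, the sponsor and the authorities (7.4.1, 7.4.2). The duty in section 9.4 to inform the ethics committee of serious device effects is thereby covered.
- *Malfunctions:* these go on a separate Device Deficiency CRF, whether or not an adverse event occurred (7.7).
- *Endpoint:* the safety outcome in 5.1.1 is worded on adverse events and device malfunctions, not on ADEs.
- *Decisions:* section 8.2 sets no statistical criterion for terminating the study, and no threshold elsewhere depends on an ADE count.

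**The case for a change.** The best case for a change starts from the wording of the scale. Not related, Possible and Causal are written in terms of timing and causes; Unlikely and Probable share a different pattern, built on the relevance of the relationship and on further information. That fits a three-level scale (not related, possibly related, related) to which two levels were added without updating the rule. *Related* would then correspond to Causal, and Probable would have no stated place. Two sites could rate the same event differently, and on that reading the difference would alter its ADE status. Device attribution matters in a small single-arm study, and the repair would be one sentence and two definitions.

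Part of this stands. The protocol does not write the cut-off in the scale's own labels, and the two top definitions are not cleanly separated. An analysis plan could settle the tabulation but not the rating definitions.

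The rest does not carry. The drafting history is an inference. Even if it is right, excluding Probable would give a rule that includes Possible, omits Probable and includes Causal, against section 7.1. The sponsor's responsibility for classification in 7.4.2 limits variation between sites. The expectation in section 3 concerns serious events, for which reporting does not depend on the causality level, whereas any effect of the wording would fall mainly on non-serious ADEs. The shift of 3.3 points presupposes that a Probable event is left out.

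**Conclusion.** This is a clerical slip with one sensible reading: Possible, Probable and Causal all make an event an ADE, or a SADE if serious. On that reading harmonising the words changes the status of no event. On any reading no event goes unrecorded, no serious event is reported differently, and neither the safety endpoint nor any decision rule is touched. What remains is that raters may differ between Probable and Causal, a distinction on which the protocol builds no analysis. No change to the plan is called for.

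The conclusion assumes that the adverse event CRF, which is not shown, records the relationship on the five levels of section 7.2, and that no analysis outside the protocol separates Probable from Causal. Because the rating is to be obtained for every event, an analyst can apply the cut-off of Possible or higher directly and state it in a table footnote.
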